2.5 Genomic testing in de-novo AML

The Therapeutically Applicable Research to Generate Effective Treatments (TARGET) initiative was launched by the National Cancer Institute to support genomic characterization of pediatric cancers with poor outcomes, AML being one of them. As a part of the Target Pediatric AML initiative (TpAML), genomic sequencing will be carried out for clinical purposes through the Foundation One Heme panel. This panel sequences DNA coding regions of 406 genes and selected introns of 31 genes involved in hematologic malignancies. It also performs RNA sequencing of 265 genes commonly rearranged in cancer. All patients on this study will have Foundation One Heme panel sent at diagnosis and we expect results to be available within 4 weeks. We will be able to correlate the data obtained from this panel with disease outcomes. While this panel includes the genes of interest for risk stratification, it is recognized that other investigational sequencing approaches may be options during the course of this trial.

3.0 STUDY DESIGN AND POPULATION

CHOA-AML is a single-center pilot trial. We will enroll up to 30 newly diagnosed pediatric patients with acute myeloid leukemia (AML) at CHOA.

All clinical and laboratory data required for determining eligibility of a patient enrolled must be available in the patient's medical/research record which will serve as the source document for verification.

All clinical and laboratory studies to determine eligibility must be performed within 7 days prior to enrollment unless otherwise indicated. Bone marrow aspiration (BMA)/biopsy must be obtained within 2 weeks prior to start of protocol therapy (repeat the BMA/biopsy if necessary).

3.1 Patient Inclusion Criteria

3.1.1 **Age:** Patients must be less than 21 years of age at the time of study enrollment

3.1.2 **Diagnosis:** Patients must be newly diagnosed with AML

3.1.1.1 Patients with previously untreated primary AML who meet the customary criteria for AML with $\geq 20\%$ bone marrow blasts as set out in the 2016 WHO Myeloid Neoplasm Classification are eligible.

3.1.1.2 Attempts to obtain bone marrow either by aspirate or biopsy must be made unless clinically prohibitive. In cases where it is clinically prohibitive, peripheral blood with an excess of 20% blasts and in which adequate flow cytometric and cytogenetics/FISH testing is feasible can be substituted for the marrow exam at diagnosis.

3.1.1.3 Patients with <20% bone marrow blasts are eligible if they have:

- A karyotypic abnormality characteristic of *de novo* AML (*t*(8;21)(q22;q22), *inv*(16)(*p13q22*) or *t*(16;16)(*p13;q22*) or,
- the unequivocal presence of megakaryoblasts, or
- Biopsy proven isolated myeloid sarcoma (myeloblastoma; chloroma, including leukemia cutis)

3.1.3 **Performance Level:** Patients with acceptable organ function and any performance status are eligible for enrollment

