3.4 Aflac Office Monitoring Schedule

The trial will be monitored internally according to the following schedule:

- Study monitoring will occur every 6 months until all subjects have completed intervention;

- Once all subjects have completed intervention, a final monitoring visit will occur within 90 days after the last study related procedures and follow-up are completed for all patients enrolled;
- Additional monitoring may be performed in the event of serious adverse event(s), if deemed necessary by the monitoring committee or if requested by the Principal Investigator.

4.0 **RISK STRATIFICATION**

After completion of first course of chemotherapy (Induction I), patients will be classified into low or high-risk groups.

Low risk

t(8;21)(q21.3;q22) – CBF (*RUNX1-RUNX1T1*)
 inv(16)/t(16;16)(p13.1q22.1) – CBF (*CBFB-MYH11*)
NPM1 positive without associated *FLT3* mutation
Biallelic CEBPA positive
 No High-Risk Prognostic Markers/MRD negative (<0.05%) at end of 1st induction
CBF, CEBPa, NPM positive **and** MRD positive at the end of 1st Induction

High risk

inv(3)(q21q26.3) *MECOM-RPN1* fusion
 t(3;21)(26.2;q22)
 t(3;5)(q25;q34)
 t(6;9)(p23;q34.1)(*DEK-NUP214*)
 t(8;16)(p11.2;p13.3) *KAT6A*(8p11.21) Fusion (for patients who are 90 days or older)
 t(16;21)(p11;q22) *FUS-ERG*
 Inv(16) (p13.3q24.3) *CBFA2T3-GLIS2*
 Monosomy 7
 Monosomy 5/5q-[*EGR1*(5q31) deleted]
KMT2A(*MLL*) (11q23.3)

- t(4;11)(q21;q23)
- t(6;11)(q27;q23)
- t(10;11)(p11.2;q23)
- t(10;11)(p12;q23)
- t(11;19)(q23;p13.3)

 11p15 rearrangement - *NUP98* (11p15.5)
 12p 13.2 rearrangement - *ETV6* – any partner gene
 Deletion 12p to include 12p13.2
FLT3 High Allelic Ratio mutations (AR >0.1)
 10p12.3 rearrangement - *Non-KMT2A MLL T10 Fusions*
 RAM phenotype (high CD56, dim-to-negative expression CD45 & CD38, no HLA-DR)
 MRD positive (>0.05%) at end of 1st induction, excluding those with *CBF, CEBPa, NPM*

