8.1 EVALUATIONS/DATA TO BE ACCESSIONED

STUDIES TO BE OBTAINED	Baseline	Each Course of chemotherapy	End of therapy	Relapse/Refractory
History	X	---	---	---
Physical Exam	X	X	X	X
Vital Signs	X	X	X	X
Height, Weight, BSA	X	X	X	X
Performance status	X	X	X	X
CBC with differential, platelets	X	X	X	X
Liver Function – AST, ALT, Total and Direct Bilirubin, Total Protein, Albumin	X	X	X	X
Kidney Function – BUN, Creatinine	X	X	X	X
Electrolytes (Sodium, Potassium, Chloride, Calcium, Magnesium, Phosphorous) and Glucose	X	X	X	X
Chest X-ray and Pulse oximetry	X	---	---	X
ECHO and EKG	X	X Prior to each course	X	X
Bone marrow aspirate (BMA) and/or biopsy for morphology and flow cytometry to include CD33 expression	X	---	---	X
BMA for FLT3 testing	X	---	---	X
BMA for CD33 Genotype	X	---	---	---
BMA for genomic testing	X	---	---	X
Lumbar Puncture with cell count and cytospin	X	---	---	X
Imaging of chloroma –CT/MRI if applicable	X	---	---	X
BMA for MRD testing	--	X End of each course	X	--
Concomitant Medication Data	X	X	X	X
Adverse Event/Toxicity Monitoring		X	X	

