11.1 STATISTICAL CONSIDERATIONS

Sample size: This is a pilot study aimed at utilizing a risk-stratified approach along with pharmacogenomics to treat newly diagnosed patients with AML. Annually we expect to have 10-20 de novo AML patients to be diagnosed and treated at our institution. This two-year study would be expected to enroll approximately 30 patients (both low and high risk) during that time period. As a pilot study, this trial is not hypothesis-driven but rather estimation-driven, and the sample size is based on a feasible two-year target for our institution.

Descriptive statistics will be conducted for demographic and patient characteristic variables, including toxicity related variables. Mean and standard deviation will be used for continuous variables and frequency and percent will be used for categorical variables.

Primary Endpoints:

1. Event-free survival: Event-free survival (EFS) is defined as the time from on study to death, failure to achieve remission or relapse, where those patients who do not experience these events will be censored at last follow-up date. EFS will be estimated using the Kaplan-Meier method for newly diagnosed patients with pediatric acute myeloid leukemia using a risk stratified approach.

Secondary Endpoints:

1. Disease-free survival: Disease-free survival (DFS) from end of first course of therapy is defined as time from end of first course of therapy to death or relapse, where those patients who do not experience these events will be censored at last follow-up date. DFS will be estimated using the Kaplan-Meier method for newly diagnosed patients with pediatric acute myeloid leukemia using a risk stratified approach.
2. Overall survival: Overall survival (OS) is defined as (1) time from study entry and (2) from end of first course of therapy to death, where those who do not die will be censored at

last follow-up date. OS will be estimated using the Kaplan-Meier method for newly diagnosed patients with pediatric acute myeloid leukemia using a risk stratified approach.

3. Minimal residual disease: Minimal residual disease (MRD) is the proportion of patients that are in remission (MRD negative) after one cycle of induction chemotherapy in both the GO and non-GO groups. Descriptive statistics (frequency and percent) will be used to estimate the frequency of MRD.

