4. Disease-free-survival MRD negative: Disease-free-survival, defined as time from end of first course of therapy to death or relapse, will be estimated for MRD negative patients who lack high or low risk molecular and cytogenetic features using the Kaplan-Meier method.
5. Cardiac ejection fraction: Descriptive statistics (frequency and percent) will be used to estimate the frequency of patients that develop cardiac ejection fraction <50% (CTCAE V5.0 grade 2 or greater dysfunction) either during therapy (early cardiotoxicity) or after completion of therapy (late cardiotoxicity).

Exploratory Endpoints:

1. Molecular abnormalities: Descriptive statistics will be used to describe the molecular abnormalities seen in de-novo AML samples using comprehensive genomic testing.

Analysis Datasets:

All eligible patients who receive at least one dose of protocol therapy will be included in the primary efficacy analysis. Safety analysis will be conducted using the Safety Population, defined as any participant receiving at least one dose of study treatment.

Interim Analysis:

The rates of infectious and hematologic toxicities with each chemotherapy course are well established from prior COG study AAML0531 (refer to table below). These toxicity rates will be monitored after enrollment of the first 10 patients and subsequently after the next 10 patients are enrolled. While this is highly unlikely to happen, if toxicity rates are exceeding those expected for each course, the study will be stopped.

AAML0531	ADE	ADE +GO	MA	AE	Capizzi
Infection incidence					
Documented infection	35 %	36 %	69%	49 %	67%
Neutropenic fever	31 %	32 %	23%	23 %	18%
Hematologic Recovery (days)					
Median time to platelets >50K	26	28	38	25	42
Median time to ANC >500	30	30	37	27	40

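### The course 1 MRD endpoint has no marrow-evaluable denominator, so isolated myeloid sarcoma patients with uninvolved marrow would count as MRD-negative successes whatever their tumour response

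*Combined protocol and SAP*

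**What the plan says.** **Eligibility.** Item 3.1.1.3 in Section 3.1 opens with "Patients with <20% bone marrow blasts are eligible if they have" and lists as one qualifying condition "Biopsy proven isolated myeloid sarcoma". It sets no minimum marrow blast count and does not require marrow involvement.

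**Measurement.** The Section 8.1 table has a row "BMA for MRD testing", ticked at the end of each course and at end of therapy. No other specimen is listed for MRD. FLT3 testing ("BMA for FLT3 testing") and genomic testing are also listed on marrow aspirate. CT or MRI of a chloroma is ticked at baseline and at relapse or refractory disease, but not for each course or at end of therapy.

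**Endpoint.** Section 11.1, secondary endpoint 3, is the "proportion of patients that are in remission (MRD negative) after one cycle of induction chemotherapy in both the GO and non-GO groups". Secondary endpoint 4 is DFS in MRD-negative patients without high-risk or low-risk molecular and cytogenetic features.

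**Analysis sets.** Section 11.1 defines two. One is a safety population of all treated patients. The other is given by "All eligible patients who receive at least one dose of protocol therapy will be included in the primary efficacy analysis". No MRD-evaluable set is defined.

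**Extramedullary disease.** Section 4.0 places patients without high-risk markers in low risk if they are "MRD negative (<0.05%) at end of 1st induction", and has no extramedullary criterion. Sections 5.3 and 5.4 say that both MRD and extramedullary disease go into the response determination used to assign the risk stratum. Section 10.2, item 1, counts extramedullary disease as failure to attain remission, there after Induction II.

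**The concern.** Marrow MRD measures response only if there was leukemia in the marrow to clear. For a patient whose disease at diagnosis was confined to a sarcoma, a negative marrow after Induction I would have been negative without treatment. Endpoint 3 equates that result with remission, so the patient is scored a success even if the tumour persists.

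Two estimates are exposed. The first is the MRD-negative proportion described separately for the GO and non-GO groups. GO is given by CD33 genotype, so such a patient can fall in either group and shift one proportion but not the other. The second is DFS in MRD-negative patients without high-risk or low-risk features. A sarcoma patient with an uninvolved marrow and no detected marker meets that definition, although the MRD result says nothing about response.

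The trial is described as estimation-driven, so these proportions and curves are themselves the results.

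**Working it through.** **1. Planned size.** Section 11.1 expects 10–20 patients a year for two years: 2 × 10 = 20 to 2 × 20 = 40, midpoint 2 × 15 = 30. The stated figure of about 30 is reproduced. No power calculation applies.

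**2. Size of the GO group.** Section 2.2 reports, for AAML0531, 256 of 816 patients with CT or TT genotype and CD33 expression in quartiles 2–4, and 61 of 816 with CC genotype in quartile 1. Taking quartile 1 as 816/4 = 204 (an assumption):
- CT/TT = 256 + (204 − 61) = 399
- CC = 816 − 399 = 417, and 417/816 = 51.1%
- 30 × 0.511 = 15.3, so about 15 patients in each group.

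**3. Bias.** Let N be the patients counted, k those with uninvolved marrow scored negative, and p the true MRD-negative rate in the other N − k.

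Observed rate = [p(N − k) + k]/N

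Bias = observed rate − p = (k/N)(1 − p)

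This is never negative, and is positive whenever k ≥ 1 and p < 1. The documents give neither k nor p, so both are assumed.

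| N | k | p = 80% | p = 50% |
|---|---|---|---|
| 15 | 1 | 1.3 points | 3.3 points |
| 15 | 2 | 2.7 points | 6.7 points |
| 30 | 1 | 0.7 points | 1.7 points |
| 30 | 2 | 1.3 points | 3.3 points |
| 30 | 3 | 2.0 points | 5.0 points |

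**4. Whole-number illustrations, with exact (Clopper-Pearson) 95% intervals.**
- One group, k = 1: 10/15 = 66.7% (38.4–88.2) becomes 9/14 = 64.3% (35.1–87.2).
- One group, k = 2: 10/15 = 66.7% becomes 8/13 = 61.5% (31.6–86.1).
- Whole cohort, k = 2: 20/30 = 66.7% (47.2–82.7) becomes 18/28 = 64.3% (44.1–81.4).

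The interval half-widths are about (88.2 − 38.4)/2 = 25 points at n = 15 and (82.7 − 47.2)/2 = 18 points at N = 30.

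**5. How likely such a patient is.** The frequency of marrow-uninvolved sarcoma is not in the documents. At an assumed 1–5%, the expected number among 30 is 0.3–1.5. The chance of at least one is 1 − 0.99^30 = 26% to 1 − 0.95^30 = 79%. The chance of two or more in one group of 15 is about 1–17%.

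**6. DFS subgroup.** Its size is not stated. If it held 8–10 patients (an assumption), one such patient would be 1/10 = 10% to 1/8 = 12.5% of it. The direction of any effect on DFS cannot be derived from the documents.

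**7. The four places on extramedullary disease, side by side.**

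| Place | Role of extramedullary disease |
|---|---|
| Section 4.0 | none; markers and marrow MRD only |
| Sections 5.3, 5.4 | part of the response determination that assigns the stratum |
| Section 10.2, item 1 | its presence is failure to attain remission, after Induction II |
| Section 8.1 | no chloroma imaging scheduled at the end of a course |

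Endpoint 3 follows Section 4.0 in using marrow MRD alone, but calls the result remission, which Section 10.2 treats more broadly.

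**The case against.** The strongest reply is that the plan never says these patients are counted as MRD negative. The all-treated sentence governs the primary efficacy analysis, which is EFS, so the MRD denominator is unspecified rather than wrongly specified. That stands as a description. But the endpoint speaks of patients in each GO group without restriction, so the plain reading includes them, and the alternative is to choose a denominator after seeing results.

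Section 10.2 suggests that the protocol's idea of remission covers extramedullary disease, so a patient with persisting tumour is arguably not in remission. But that item applies after Induction II and does not settle an endpoint read after course 1.

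Two stronger readings are tempting, and the documents do not support them.
- A reader might infer that every patient enrolled with isolated sarcoma is negative by construction. The eligibility route covers any marrow blast percentage below 20%. Against a 0.05% threshold, low-level involvement is measurable, and MRD then carries information.
- A reader might infer that these patients necessarily default to low risk. A high-risk marker overrides MRD negativity in Section 4.0, Sections 5.3 and 5.4 intend extramedullary disease to inform the stratum, and Section 10.3, item 7, takes a patient off study if FLT3/ITD status is unknown at the end of Induction I. What can be shown is an incomplete cross-reference.

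Finally, the size is small. There may well be no such patient: at the assumed 1–5% frequency, the chance of none among 30 is 21–74%. No decision rule uses the MRD proportion. All of this stands and limits the weight of the point.

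**Conclusion.** The concern holds for patients whose marrow is uninvolved at diagnosis, and only for them. As worded, endpoint 3 scores such a patient as a success whatever the tumour response, and the same patient could enter the MRD-negative DFS subgroup.

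The direction is certain once one such patient is counted and p is below 1. The size rests on assumed values: for p between 50% and 80%, 1.3–3.3 points for one patient and 2.7–6.7 for two in a group of about 15, and nothing if none enrol. This is well inside sampling error at this sample size and would not change a reader's overall view of the regimen. It is still avoidable and runs one way, and it could fall on only one side of the GO versus non-GO description. The inconsistency over extramedullary disease remains whatever the number of patients.

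Rating: a cheap improvement.

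**What to change.** In Section 11.1:
- Define the MRD-evaluable set as patients with leukemia detectable by flow cytometry at diagnosis in marrow, or in blood where item 3.1.1.2 allows blood to replace the marrow examination. Section 8.1 already schedules baseline marrow flow cytometry.
- Use that set for the MRD-negative proportion in the GO and non-GO groups.
- Report sarcoma patients with uninvolved marrow separately, by extramedullary response.
- Keep the MRD-negative DFS subgroup as assigned under Section 4.0, so that the estimate matches the group formed by the protocol, and report it with and without these patients.

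Sections 4.0, 5.3/5.4, 10.2 item 1 and the Section 8.1 imaging schedule must be reconciled on how extramedullary disease enters response and risk assignment. This review does not propose which clinical rule should apply.

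The cost is a few lines of SAP text, and an MRD denominator lower by perhaps 0–2 patients.

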3.2 Patient Exclusion Criteria

3.2.1 Patients with any of the following constitutional conditions are not eligible:

- Fanconi anemia
- Shwachman syndrome
- Any other known bone marrow failure syndrome
- Patients with constitutional trisomy 21 or with constitutional mosaicism of trisomy 21

Note: Enrollment may occur, pending results of clinically indicated studies to exclude these conditions.

3.2.2 Other Excluded Conditions:

- Any concurrent malignancy
- Juvenile myelomonocytic leukemia (JMML)
- Philadelphia chromosome positive AML
- Biphenotypic or bilineal acute leukemia
- Acute promyelocytic leukemia (APL)
- Acute myeloid leukemia arising after a clearly defined preceding myelodysplastic syndrome
- Therapy-related myeloid neoplasms

Note: Enrollment may occur pending results of clinically indicated studies to exclude these conditions.

3.2.3 Sexually Active Patients

Sexually active patients of reproductive potential are not eligible unless they have agreed to use an effective contraceptive method for the duration of their study participation.

3.2.4 Pregnancy and Breast Feeding:

- Female patients of childbearing potential are not eligible unless a negative pregnancy test result has been obtained
- Female patients who are pregnant are ineligible since fetal toxicities and teratogenic effects have been noted for several of the study drugs.
- Lactating females are not eligible unless they have agreed not to breastfeed their infants.

3.3 Definitions

3.3.1 CNS LEUKEMIA AT DIAGNOSIS:

CNS disease at diagnosis is defined as:

- Any number of blasts on a cytopsin prep in an atraumatic (< 100 RBCs) lumbar puncture.
- Blasts in a traumatic tap in which the WBC/RBC ratio in the CSF is twice that in the peripheral blood.
- Clinical signs of CNS leukemia (such as facial nerve palsy, brain/eye involvement or hypothalamic syndrome). Extra-ocular orbital masses are not considered CNS leukemia.
- Radiographic evidence of an intracranial, intradural mass consistent with a chloroma.

3.3.2 Method of Evaluation for Traumatic Lumbar Punctures

If the patient has leukemic cells in the peripheral blood and the lumbar puncture is traumatic and contains blasts, the following algorithm should be used to diagnose CNS disease:

$$\frac{\text{CSF WBC}}{\text{CSF RBC}} > 2X \quad \frac{\text{Blood WBC}}{\text{Blood RBC}}$$

A patient with CSF blasts, whose CSF WBC/RBC is 2X greater than the blood WBC/RBC ratio, has CNS disease at diagnosis. Example: CSF WBC = 60/ μ L; CSF RBC = 1,500/ μ L; blood WBC = 46,000/ μ L; blood RBC = 3 X 106/ μ L:

$$\frac{60}{1,500} = 0.04 \quad > 2X \quad \frac{46,000}{3 \times 106} = 0.015$$

3.3 Protection of Human Subjects

This protocol will be reviewed and approved by the Emory University Institutional Review Board (IRB) prior to study initiation. Prospective participants and their families will be informed of the nature of the study and will be given pertinent information as to the intended purpose, possible benefits, and possible adverse events. The procedures and possible hazards to which the patient will be exposed will be explained, as well as alternatives to participation in this trial will be presented in detail to the patient and to the patient's responsible family members. An approved informed consent statement will be read and signed by the patient (or responsible family member if under the age of 18) and an investigator.

Verbal assent will be obtained from children ages 6 to 10 and documented in the patients' medical record, as well as being noted in the case report forms. Written assent will be obtained from children ages 11 to 17, using an approved assent statement, along with use of the informed consent by their parent or guardian. Participants 18 years or older will read/sign the consent form.

3.4 Aflac Office Monitoring Schedule

The trial will be monitored internally according to the following schedule:

- Study monitoring will occur every 6 months until all subjects have completed intervention;

- Once all subjects have completed intervention, a final monitoring visit will occur within 90 days after the last study related procedures and follow-up are completed for all patients enrolled;
- Additional monitoring may be performed in the event of serious adverse event(s), if deemed necessary by the monitoring committee or if requested by the Principal Investigator.

4.0 **RISK STRATIFICATION**

After completion of first course of chemotherapy (Induction I), patients will be classified into low or high-risk groups.

Low risk

t(8;21)(q21.3;q22) – CBF (*RUNX1-RUNX1T1*)
 inv(16)/t(16;16)(p13.1q22.1) – CBF (*CBFB-MYH11*)
NPM1 positive without associated *FLT3* mutation
Biallelic CEBPA positive
 No High-Risk Prognostic Markers/MRD negative (<0.05%) at end of 1st induction
CBF, CEBPa, NPM positive **and** MRD positive at the end of 1st Induction

High risk

inv(3)(q21q26.3) *MECOM-RPN1* fusion
 t(3;21)(26.2;q22)
 t(3;5)(q25;q34)
 t(6;9)(p23;q34.1)(*DEK-NUP214*)
 t(8;16)(p11.2;p13.3) *KAT6A*(8p11.21) Fusion (for patients who are 90 days or older)
 t(16;21)(p11;q22) *FUS-ERG*
 Inv(16) (p13.3q24.3) *CBFA2T3-GLIS2*
 Monosomy 7
 Monosomy 5/5q-[*EGR1*(5q31) deleted]
KMT2A(*MLL*) (11q23.3)

- t(4;11)(q21;q23)
- t(6;11)(q27;q23)
- t(10;11)(p11.2;q23)
- t(10;11)(p12;q23)
- t(11;19)(q23;p13.3)

 11p15 rearrangement - *NUP98* (11p15.5)
 12p 13.2 rearrangement - *ETV6* – any partner gene
 Deletion 12p to include 12p13.2
FLT3 High Allelic Ratio mutations (AR >0.1)
 10p12.3 rearrangement - *Non-KMT2A MLL T10 Fusions*
 RAM phenotype (high CD56, dim-to-negative expression CD45 & CD38, no HLA-DR)
 MRD positive (>0.05%) at end of 1st induction, excluding those with *CBF, CEBPa, NPM*

